## INTRODUCTION

Poor sleep quality is a prevalent and global health problem. Roughly one-third of the world's population reports insufficient sleep duration and as much 70% report poor quality or non-restorative sleep which can have cascading impacts on an individual's health and wellbeing, including increased risk for cardiovascular morbidity and mortality, depression, and accidents. Beyond these individual health consequences, there are also substantial societal implications of poor sleep quality. Insomnia is associated with reduced productivity in the workplace due to absenteeism and presenteeism, resulting in the loss of an average of 44–54 working days per year. A recent RAND report estimated the economic losses associated with insomnia in several of the world's largest economies, including an estimated \$207.5 billion dollar loss annually.

Given the profound consequences to public health and the economy, it is important to identify novel and scalable treatment options to aid the millions of individuals worldwide experiencing poor sleep quality. Importantly, the front-line treatment for insomnia is cognitive-behavioral therapy for insomnia. However, this treatment remains underutilized due to a combination of factors, including a lack of specialty trained providers and lack of time and resources by both providers and patients. Furthermore, the typical course of behavioral treatment for insomnia is 6 to 8 sessions, which may be a time burden for many patients, especially for in-person treatment. Moreover, from a prevention perspective, there is an acute need to identify safe, effective, and non-invasive treatments to improve sleep quality, in those experiencing poor sleep quality though not necessarily meeting diagnostic criteria for clinical insomnia. This perspective is also consistent with current recommendations to consider sleep health on a continuum, as opposed to discrete clinical disorders only, and to promote sleep health across the continuum.

Recognizing this need, the current study investigates a novel device (Evolv28) designed to improve sleep through the application of variable weak magnetic frequencies. Evolv28 is a wearable sleep wellness device that contains coils that emits variable complex weak magnetic fields (VCMFs) through a neckband. The device is classified as a low-risk wellness device that does not require FDA approval.

Variable weak magnetic frequencies are proposed to interact with neural activity by subtly altering the brain's electromagnetic environment. Results of a pilot study testing Evolv28 suggest that device users may experience reductions in perceived stress and anxiety. Given strong associations between stress, anxiety, and poor sleep quality, the application of variable weak magnetic fields may also have benefits for sleep quality. Preliminary studies have indicated that these frequencies can influence brainwave patterns associated with different sleep stages, suggesting their potential to enhance the restorative aspects of sleep. By targeting specific frequencies, it may be possible to facilitate transitions between sleep stages, potentially helping to consolidate sleep (i.e., improve sleep efficiency) and improve sleep quality.

The goal of the current study was to conduct a randomized pilot study to evaluate the efficacy of the Evolv28 device for improving sleep quality among individuals reporting poor sleep quality. If successful, this intervention could represent a novel and scalable solution to the widespread global problem of poor sleep quality and its downstream consequences.

## METHOD

### **Study Design**

The study was a randomized, double blinded, placebo-controlled trial with 4-week intervention followed by a two-month open label follow-up period. This study was approved by the University of Utah Institutional Review Board (IRB\_00165943) and registered on clinicaltrials.gov (<https://clinicaltrials.gov/study/NCT05952297>).

### **Participants**

Participants were recruited from the United States via social media advertising and the University of Utah research study locator portal. Inclusion criteria included the following: age 18-65, read and write in English, smartphone user and reporting moderate to severe insomnia symptoms, defined as an

Insomnia Severity Index score of  $\geq 15$ . Participants were excluded if they had diagnosed sleep disorders other than insomnia (e.g., sleep apnea or restless legs syndrome) or were currently receiving additional treatment for insomnia (e.g., hypnotic medication, cognitive behavioral therapy, etc.). Further exclusion criteria include a history of serious mental health conditions (e.g., Patient Health Questionnaire 8 score of  $>15$ , psychosis, Bipolar I or the use of antipsychotic or mood stabilizing drugs), serious physical conditions (e.g., current cancer treatment, neurological illness), drug use (as defined by  $>14$  alcoholic beverages per week, the use of cannabis  $>3$  times in the past month, any use of illicit street drugs), caffeine intake of  $>400$ mg per day, overnight work more than once a month, frequent moderate to severe migraine attacks or headaches, pregnancy, and traveling across time zones  $>3$  times throughout the study period.

### **Procedure**

All study procedures were performed remotely. Interested participants completed a screening survey, then if eligible, a study coordinator contacted the participant via email to review study information and schedule a time to complete informed consent. Upon completion of informed consent, study materials were sent to the participant that consisted of the Evolv28 device (inactive), a Fitbit and device instructions. Upon receipt of the study materials, participants completed an instructional meeting with study staff, where they reviewed baseline procedures and Fitbit setup. Participants then completed online surveys, 7 days of daily electronic sleep diary surveys (SurveySignal) and wore the Fitbit for 7 days.

After participants completed their baseline week, a staff member, who was not associated with the study, determined each participant's group assignment and then sent that participant's device serial number to programmers. Participants were randomized 1:1 between intervention and control groups. The randomization table was generated using a random number table stratified by gender using permuted blocks of 4 to 6 participants. Study staff and participants were both blinded to treatment group assignment. To begin the 4-week trial period, the study coordinator met with each participant to ensure the device was activated and confirmed the participant's understanding of how to use it. The intervention

group received the active program, and the control group received an inactive program. In both conditions, the device and application appeared to be active. Participants were asked to wear the device for at least 3 hours per day. If any technical issues occurred, the intervention time was extended to allow for at least four weeks of use before the post-intervention assessment. Participant adherence to the Fitbit and Evolv28 were monitored by the study statistician throughout the trial and reminders were sent to participants who were non-adherent in wearing either device for more than 2 days.

For the follow-up assessment, participants wore the Fitbit again for 7 days and completed electronic sleep diaries for 7 days. Upon completion of the 4-week trial, participants completed a set of follow-up surveys to assess changes in sleep and mood. After the post-trial assessment, all Evolv28 were transitioned to run the active treatment program between week 4 and 3 months. At the end of 3 months, participants completed online questionnaires. Participants were compensated with \$100 via an Amazon.com gift card and kept the study Fitbit and Evolv28 device.

## **Measures**

Demographics: Participants filled out a brief demographic measure that contained questions on age, sex, gender, race/ethnicity, marital status, education level, household income level, and employment status.

Insomnia Severity Index (ISI): The ISI is a widely used tool that assesses the severity of insomnia. It consists of questions that evaluate various aspects of insomnia, including difficulty sleeping, staying asleep, waking up too early, and the impact of these on daily functioning. Each question is scored 0-4 and summed, allowing for a total range of 0 to 28. Higher scores indicate a greater severity of insomnia, with 15-21 interpreted as moderate insomnia and 22-28 interpreted as severe insomnia.

Sleep Disturbance and Sleep-Related Impairment: Participants completed PROMIS sleep disturbance and sleep-related impairment, which are both 8-question adaptive measures that assess the degree to which participants have difficulty sleeping and the degree to which it impacts their lives, respectively. Raw

scores are converted to a standardized *t* score that has a mean of 50 and SD of 10. Higher scores indicate worse sleeping or impact of sleep, with scores greater than 60 considered elevated.

Functional Outcomes of Sleep Questionnaire 10-item (FOSQ-10): The FOSQ-10^16 is a 10-item assessment that assesses the impact of sleep on daily functioning, such as driving and working. Each item was scored on a 4-point Likert scale and summed. Lower scores suggest greater impairment due to sleep-related issues.

General Anxiety Disorder 7 (GAD-7): The GAD-7 is a 7-item questionnaire designed to assess the severity of generalized anxiety disorder symptoms. Each item is scored on a 4-point Likert scale. Questions indicating negative affect were coded and summed. Questions indicating positive affect were reverse scored, then summed for a total score. Higher scores indicate more severe general anxiety.

Perceived Stress Scale (PSS): The PSS is a 10-item questionnaire that measures the degree to which individuals are stressed in the past month. Each item is scored on a 5-point Likert scale. Questions indicating negative affect were coded and summed. Questions indicating positive affect were reverse scored. Higher scores indicate a greater amount of perceived stress.

Patient Health Questionnaire 8: The Patient Health Questionnaire 8 is an 8-item assessment to determine the degree to which a respondent experiences depressive symptoms. Each item corresponds to diagnostic criteria for major depressive disorder, such as little interest in doing things, or trouble concentrating. Each question is scored and added together on a 4-point Likert scale. Higher scores indicate a greater severity of depressive symptoms. Scores  $\geq 10$  indicate the presence of depressive symptoms.

Sleep Diary: Participants completed items from the Consensus Sleep diary. Items include bedtime, sleep latency, number of awakenings, total duration of awakenings, final wake time and rise time. It also

provided the opportunity to comment on any unusual event that may have occurred. Using these diaries, we calculated sleep latency, sleep duration, wake after sleep onset, and sleep efficiency. Sleep diary data was cleaned (e.g., reviewed for AM/PM errors, negative sleep efficiencies and sleep efficiencies >1) diaries were considered valid if participants had at least 4 valid days completed.

Objective sleep/wake estimation: Sleep-wake data was estimated using a Charge 5 Fitbit that was worn during the baseline week, the first week of the trial, and the last week of the trial. Fitbits are comparable to research-grade actigraphy for estimating sleep duration. Fitbit data was collected and aggregated using the Fitabase platform. Fitbit-derived sleep variables included total sleep time, wake after sleep onset (WASO) and sleep efficiency (percent asleep divided by the sleep period time). Sleep periods were auto-scored, and therefore the sleep latency variable was not valid. The sleep variables were scored by the Fitbit algorithm, using the stages algorithm (with heart rate data) when possible, and if not available using the classic (movement only) algorithm. Most days both pre and post for each group were scored using the stages algorithm (>90%) and therefore all valid days were used in the analysis. To determine a valid day, we first identified the primary sleep period. Primary sleep periods <2 h were excluded if the sleep diary did not corroborate the very short sleep period. Fitbit data were considered valid if participants had at least 4 nights of valid data.

Evolv28 adherence: Evolv28 adherence was collected via the company's dashboard. The dashboard was password protected and only study staff not associated with screening and assessments had access to this data. The dashboard contained participant ID, group assignment (intervention or control) and device usage (average and total).

Adverse events: At 4-weeks and 3-months, participants completed a measure that asked if they experienced any symptoms while wearing the sleep device, when they developed, and their degree of

severity. In addition, if participants reported to study staff any effects of the device, these were recorded in an adverse event log and if necessary, reported to the IRB.

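### Adverse events are solicited, as described, only for time spent wearing the device, so physical symptoms that start off-device depend on being volunteered and are likely under-recorded

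*Combined protocol and SAP*

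**What the plan says.** All references are to the combined protocol and SAP.

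- **Solicited route (Measures, Adverse events).** At 4 weeks and 3 months, "participants completed a measure that asked if they experienced any symptoms while wearing the sleep device, when they developed"; severity was asked as well. This is a description of the measure. The item itself is not reproduced.
- **Spontaneous route (same paragraph).** "if participants reported to study staff any effects of the device, these were recorded in an adverse event log", with onward reporting to the IRB where needed. It carries no wear-time limit.
- **Wear (Procedure).** "Participants were asked to wear the device for at least 3 hours per day". This is a minimum. Neither the time of day nor whether the device was worn in bed is stated. The dashboard recorded usage, but no usage figure is given.
- **Diary (Measures, Sleep Diary).** It "provided the opportunity to comment on any unusual event that may have occurred". Procedure places diaries in 7 days at baseline and 7 days at follow-up. Nothing says that diary comments feed the adverse event log.
- **Rationale (Introduction).** With targeted frequencies, "it may be possible to facilitate transitions between sleep stages".
- **After week 4 (Procedure).** Every device, in both arms, is switched to the active program.
- **Data analysis.** No adverse event analysis is specified.

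**The concern.** The device is meant to act on sleep and, through sleep, on how people function afterwards. An unwanted effect could plausibly appear after the device has been taken off. A question confined to wear would not elicit such a symptom, and the second route relies on the participant both linking the symptom to the device and choosing to report it.

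At stake is the completeness of the safety record. The 4-week form is the only one that compares active with inactive devices, so physical symptoms not asked about then cannot be recovered later from a controlled comparison. Any later statement that the device is well tolerated would cover less than a reader would assume.

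**Working it through.** **1. The plan's own figures.** There is none for adverse events. The only design calculation is the sample size: d = 0.74, two-sided alpha 0.05, 80% power, 30 per group. A two-sample t-test needs 29.66, rounded up to 30 per arm, and 30 per arm gives power 0.805. It reproduces and has no bearing on this point.

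**2. Where each kind of symptom would be picked up.**

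| Symptom | Solicited adverse event question | Scale with no wear limit | Adverse event log |
|---|---|---|---|
| Physical, starts during wear | Yes | No | If volunteered as a device effect |
| Physical, starts off-device (next-day headache, dizziness) | No, as described | No | If volunteered as a device effect |
| Low mood, anxiety, stress, worse sleep, daytime impairment | Only if during wear | Yes: PHQ-8, GAD-7, PSS, ISI, PROMIS, FOSQ-10 | If volunteered as a device effect |

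The gap is the second row.

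**3. Share of the day inside the question.** Share = hours worn / 24. At the requested minimum it is 3/24 = 12.5%. At assumed wear of 6, 8 or 12 hours it is 25%, 33% or 50%. Only the 3 comes from the documents, and it is a floor. This is a share of time, not a share of symptoms.

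**4. What under-recording would do (illustration).** Let p be the true proportion of participants with a given symptom and c the share of those cases recorded. Among the 28 intervention participants in Table 1, the expected number recorded is 28 × p × c, and the chance of recording at least one is 1 − (1 − p × c)^28. With p = 10%:

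| c | Expected recorded | Chance of at least one |
|---|---|---|
| 1 | 2.8 | 0.948 |
| 0.5 | 1.4 | 0.762 |
| 0.25 | 0.7 | 0.508 |
| 0.125 | 0.35 | 0.297 |

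Both p and c are assumptions; the documents give neither. Table 2 also notes three missing intervention-arm questionnaires at 1 month, so fewer than 28 may have answered.

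**5. Effect on the comparison between arms (illustration).** Assume true rates of 30% active and 15% inactive, and the same c in both arms. The recorded difference is 15 × c percentage points: 7.5 at c = 0.5 and about 1.9 at c = 0.125. The recorded ratio is (0.30 × c)/(0.15 × c) = 2.0 for every c. A filter common to both arms therefore reduces counts and the absolute difference but leaves the risk ratio alone. If a broader question adds unrelated symptoms at rate b to both arms, the ratio (0.30 + b)/(0.15 + b) moves toward 1, while the absolute difference stays at 15 points.

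**The case against.** The strongest reply is that the item wording is not in the documents. The wear phrase could be shorthand for the period of device use, and the measure also asked when symptoms developed. That stands as a reason for caution: the criticism applies to the measure as described.

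The second reply is that other routes exist. The log has no wear limit, the diary took comments, and the scales would register worsening. Table 4 shows that scales can move the wrong way: the intervention-arm change at 3 months is +0.24 on the GAD-7 and +0.6 on the PSS. This stands for mood, anxiety, stress, sleep and daytime function. It does not close the gap for physical symptoms: none of the scales is described as a general symptom checklist, and the diary ran for 7-day periods with no stated link to the log.

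Third, the study is written up in the past tense with results, so the item cannot be changed for data already collected. That stands too, and the fix allows for it. The documents also make no tolerability claim and plan no safety test between arms, which limits the present consequence.

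Several stronger readings are tempting but unsupported:

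- *Seven-eighths of harms are lost.* The 3 hours is a minimum, and unworn time is not the share of symptoms missed.
- *Overnight harms are excluded.* That would require the device to be off at night, which the documents do not say.
- *Off-device harms are missed altogether.* The spontaneous route can record them.
- *Benefits are scored around the clock while harms are not.* The same scales capture deterioration in both arms.
- *The solicited question makes blinded participants judge causality.* It filters on time. Only the spontaneous route asks for attribution.

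**Conclusion.** The point holds in a limited form. As described, solicited collection at both time points covers symptoms during wear. Physical symptoms that start off-device are recorded only when volunteered as a device effect, so under-ascertainment is likely. This rests on two assumptions: that the item reads as the Measures section describes it, and that volunteered reporting is less complete than direct questioning.

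The size of the loss cannot be computed from the documents. The figures in steps 4 and 5 show only how the loss would act over a range of assumed values. The ISI primary analysis and the sample size are not affected. It is an improvement worth making to safety collection and to how safety is reported, and it does not threaten the main result.

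**What to change.** **If the form can still be changed, or for a later study:**

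1. Ask about any new or worsened symptom since the device was activated (4-week form) or since the last survey (3-month form), whether or not the device was on at the time. Keep onset and severity.
2. Add a tick-box for timing: during wear, within 24 hours after wear, or other.
3. Log every new symptom that a participant volunteers, without requiring that it be put down to the device.
4. Compare all-symptom counts between arms at 4 weeks only, and report the during-wear subset separately. Describe the 3-month data without a controlled comparison, because all devices are by then on the active program.

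**If the data were collected with the wear-limited item:** give its exact wording, and limit any tolerability statement to symptoms during wear plus effects that participants volunteered.

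**Cost.** One online survey item and one logging instruction change. More unrelated background symptoms will be recorded in both arms, which dilutes the risk ratio somewhat. The concurrent control accounts for them at 4 weeks but not at 3 months. The reporting option costs a sentence or two.

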#### Data analysis

Data were analyzed using R version 4.2.2. We utilized descriptive statistics to describe the sample statistics at baseline. Then, we conducted linear mixed models to the effect for time and time x group interaction. The primary outcome was defined as change in ISI at 1-month. We also conducted linear mixed models to examine change over time and time x group changes from baseline to 3-months. Analyses were conducted as intention to treat and all participants who completed baseline data and were randomized were included in the mixed models. We utilized chi-square tests to evaluate percentage with a response to the intervention (decrease of 6 points or more on the ISI) and remission (ISI post-intervention score  $\leq 7$ ). An a-priori power analysis, assuming a medium-to-large effect size of  $d = 0.74$ , indicated that a total sample size of 60 participants (30 per group) would provide a power of 80% to detect significant differences with a two-sided alpha level of 0.05.

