**Table 1**

Baseline characteristics	Intervention M, SD or N, %		Control M, SD or N, %		Full sample M, SD or N, %	
Age (years)	38.9	12.5	41.6	11.8	40.4	12.1
Sex						
Female	19	68	20	65	39	66
Male	9	32	11	35	20	34
Race						
White	20	71	22	71	42	71
Asian	6	21	4	13	10	17
Black/African American	2	7	4	13	6	10
Native Hawaiian or other Pacific Islander	0	0	1	3	1	2
Ethnicity						
Hispanic/Latino	1	4	4	13	5	8
Non-Hispanic/Latino	27	96	27	87	54	92
Employment Status						
Full-time a	13	46	18	58	31	53
Part-time a	5	18	6	18	11	19
Student	3	11	3	11	6	10
Not employed	5	18	3	10	8	14
Retired	2	7	1	4	3	5
Highest level of education						
Completed high school or some high school	5	18	5	16	10	17
Associate degree or trade school	8	29	6	19	14	24
Bachelor's degree	8	29	9	29	17	29
Graduate degree	7	25	11	35	18	31

Combined yearly household income						
\$25,000 or below	3	11	6	19	9	15
\$26,000-\$50,000	6	21	4	13	10	17
\$51,000-\$75,000	8	29	6	19	14	24
\$76,000-\$100,000	4	14	6	19	10	17
>\$101,000	6	21	6	19	12	20
Prefer not to say	1	4	3	10	4	7

*Sociodemographic Characteristics of Participants at Baseline*

*Note.*  $N = 59$  ( $n = 28$  for intervention and  $n = 31$  for control). Participants were on average 40.4 years old ( $SD = 12.1$ ), and participant age did not differ by condition. a Full-time reflects 32 hours or more of work per week. Part-time reflects less than 32 hours of work per week.

Table 2. Self-Reported Outcomes at 1 Month

Assessment	Intervention						Control						$p_{between}$	$p_{within}$		
	Baseline		1-month		Change		Baseline		1-month		Change					
	M	SD	M	SD	M	SD	M	SD	M	SD	M	SD				
Insomnia Severity Index	19.1	3.3	11.8	5.2	-7.34 a	1.87	18.6	3.2	11.0	4.0	-7.58 a	.84	0.88	0.001		
PROMIS Sleep Disturbance	60.6	5.9	7.9	7.9	-6.80 a	2.02	60.8	4.9	53.5	4.9	-7.28 a	.05	0.98	0.001		
PROMIS Sleep-Related Impairment	61.0	6.1	56.0	8.0	-4.97 a	1.85	60.4	6.2	53.4	8.1	-7.02 a	1.97	0.37	0.001		
General Anxiety Disorder	7.00	4.9	5.72	4.6	-1.28 a	-0.27	6.71	4.2	4.90	3.5	-1.81 a	-0.65	0.53	0.005		
Perceived Stress Scale	16.9	6.4	15.8	7.6	-1.13	1.19	16.4	6.7	15.7	6.2	-0.76	-.49	0.87	0.44		
Functional Outcomes of Sleep	32.8	3.9	35.8	4.9	+3.05 a	1.00	31.8	5.6	35.2	4.7	+3.44 a	-0.90	0.81	0.002		

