Patient Health Questionnaire	7.40	3.6	5.4	3.6	-2.00 a	-0.07	7.7	3.6	4.7	3.4	-2.99 a	-0.23	0.39	0.001		

Note. Missing questionnaire data  $N=3$  in the intervention group and  $N=2$  for the control group.  $P_{between}=p$  value for the time x condition effect,  $p_{within}=p$  value for the time effect.

Table 3. Fitbit and Sleep Diary Outcomes at 1 Month

Assessment	Intervention						Control						$p_{between}$	$p_{within}$		
	Baseline		1-month		Change		Baseline		1-month		Change					
	M	SD	M	SD	M	SD	M	SD	M	SD	M	SD				
Sleep diary																
Sleep duration (h)	6.36	1.77	6.89	2.08	+0.53 a	+0.30	6.36	1.5	6.64	1.86	+.28 a	+0.34	0.25	0.046		
Wakefulness after sleep onset (m)	34.8	53.4	28.8	49.8	-6.0	-3.39	29.3	44.4	31.8	42.0	+2.4	-2.67	0.37	0.73		
Efficiency (%)	75.0	0.16	79	0.15	+0.04	-0.01	78.0	0.14	77.0	0.16	-0.01	+0.02	0.03	0.90		
Sleep latency (m)	43.2	46.2	39	42.0	-4.2	-4.69	41.4	41.4	43.2	52.2	+1.8	+10.70	0.07	0.63		
Fitbit																
Sleep Duration (h)	6.28	0.58	6.47	1.02	+0.19	+0.43	6.37	0.88	6.47	1.45	+0.1	+0.57	0.80	0.70		
Wake after sleep onset (m)	48.8	8.1	51.4	17.7	+2.6	+9.60	50.9	17.2	49.8	16.9	-0.9	-0.33	0.46	0.74		
Efficiency (%)	93.6	2.6	92.9	5.8	-0.7	+3.22	93.9	2.4	94.1	2.80	+0.2	+0.34	0.55	0.81		

*Note.* Missing data for actigraphy (n=23), missing data for sleep diaries (n= ).  $p = p_{between} = p$  value for the time x condition effect,  $p_{within} = p$  value for the time effect.

Table 4. Results of Self-Reported Outcomes at 3-Months

Assessment	Intervention						Control						$p_{between}$	$p_{within}$		
	Baseline		3-month		Change		Baseline		3-month		Change					
	M	SD	M	SD	M	SD	M	SD	M	SD	M	SD				
Insomnia Severity Index	19.1	3.3	11.2	4.7	-7.98 a	+1.36	18.6	3.2	9.3	4.5	-9.31 a	+1.29	0.360	0.001		
PROMIS Sleep Disturbance	60.6	5.9	53.7	8.0	-6.84 a	+2.16	60.8	4.9	52.4	6.5	-8.37 a	+1.67	0.478	0.001		
PROMIS Sleep-Related Impairment	61.0	6.1	56.2	9.4	-4.81 a	+3.30	60.4	6.2	52.6	9.1	-7.84 a	+2.94	0.246	0.001		
General Anxiety Disorder	7.0	4.85	7.24	5.6	+0.24	+5.06	6.71	4.2	5.13	5.4	-1.58	+5.83	0.284	0.338		
Perceived Stress Scale	16.9	6.37	17.5	7.6	+0.6	+1.23	16.4	6.7	15.0	7.8	-1.4	+1.10	0.254	0.227		

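### The primary 1-month ISI comparison names no baseline-ISI or gender term and appears unadjusted; a post hoc adjusted estimate costs little and may narrow the confidence interval

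*Combined protocol and SAP*

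**What the plan says.** The Data analysis section states: "The primary outcome was defined as change in ISI at 1-month". For the analysis it states that "we conducted linear mixed models to the effect for time and time x group interaction". It gives no formula, covariate list or covariance structure. The note to Table 2 defines the between-group p-value as the "value for the time x condition effect".

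On randomisation, the Procedure section says: "The randomization table was generated using a random number table stratified by gender using permuted blocks of 4 to 6 participants". Neither gender nor baseline ISI is named as a model term anywhere.

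Table 2 gives ISI mean (SD) of 19.1 (3.3) falling to 11.8 (5.2) in the intervention arm, change -7.34, and 18.6 (3.2) falling to 11.0 (4.0) in the control arm, change -7.58. The between-group p is 0.88, and no confidence interval is tabulated. The note adds: "Missing questionnaire data $N=3$ in the intervention group and $N=2$ for the control group". With 28 and 31 participants in Table 1, that leaves 25 and 29 observed at 1 month.

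**The concern.** A difference in change subtracts the baseline score with a weight of exactly 1. That weight is efficient only when the regression slope of the 1-month score on baseline is 1. Here the scores are more spread out at 1 month than at baseline, so the slope is 1 only at a fairly high correlation. At lower correlations, subtracting the whole baseline adds noise that adjustment would avoid.

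The stake is the width of the interval, not the direction of the result. In a null trial with 54 observed, the useful question is which effects remain possible, and a p-value of 0.88 does not answer it. Separately, an analysis that omits the stratification factor does not match how participants were randomised.

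**Working it through.** **Inputs.** ISI means, SDs and p-values come from Tables 2 and 4. Observed numbers (25 and 29) come from Table 1 and the Table 2 note. The baseline to 1-month correlation, rho, is not given, so it is an assumption shown as a range.

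Pooled SDs:
- baseline: s0 = sqrt[(24×3.3² + 28×3.2²)/52] = 3.25
- 1 month: s1 = sqrt[(24×5.2² + 28×4.0²)/52] = 4.59
- f = sqrt(1/25 + 1/29) = 0.273

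**Step 1: which contrast was fitted?**

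The 1-month difference in change is -7.34 - (-7.58) = +0.24. Its SE is f × sqrt(s0² + s1² - 2·rho·s0·s1), which is 1.535 at rho = 0. This gives p = 0.876, against 0.88 reported.

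The baseline-adjusted difference is (11.8 - 11.0) - b×(19.1 - 18.6), with b = rho·s1/s0 and SE = f × s1 × sqrt(1 - rho²).

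At 3 months (Table 4; one missing, so 58 observed) the difference in change is -7.98 - (-9.31) = 1.33. These data serve only to identify the model, because by then "all Evolv28 were transitioned to run the active treatment program between week 4 and 3 months". The adjusted 3-month p-values below use the change plus the 0.5-point baseline gap.

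| rho | 1 month, change p | 1 month, adjusted p | 3 months, change p | 3 months, adjusted p |
|---|---|---|---|---|
| 0 | 0.876 | 0.53 | 0.372 | 0.14 |
| 0.3 | 0.854 | 0.63 | 0.293 | 0.17 |
| 0.5 | 0.831 | 0.68 | 0.22 | 0.16 |
| 0.7 | 0.790 | 0.74 | 0.129 | 0.13 |
| reported | 0.88 | 0.88 | 0.360 | 0.360 |

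Building the 1-month adjusted estimate from the change plus the baseline gap (0.24 + 0.5 = 0.74 before adjustment) gives p = 0.56 to 0.79 instead. Building the 3-month one from the tabulated means (11.2 - 9.3 = 1.9) gives 0.11 to 0.15. Over all correlations the adjusted 3-month p peaks at about 0.17. An adjusted 1-month p near 0.88 would need rho of about 0.94 to 0.96.

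The reported values therefore fit the unadjusted contrast, but only with rho near 0. A model that ignored the pairing of visits would print the same p at any true rho. Allowing for rounding of the p-value, the difference and the SDs, the 1-month p is compatible with rho of about -0.31 to 0.13. For both reasons it should not be used to estimate rho.

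**Step 2: what would adjustment gain?**

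Var(change) - Var(adjusted) = (s0² + s1² - 2·rho·s0·s1) - s1²(1 - rho²) = (s0 - rho·s1)². This is never negative, and it is zero at rho = 3.25/4.59 = 0.71. The half-widths below are means from simulation (6,000 runs per rho), with the baseline slope estimated and gender fitted but given no effect.

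| rho | SE, change | SE, adjusted | 95% CI half-width (ISI points) | Effect |
|---|---|---|---|---|
| 0 | 1.535 | 1.253 | 3.07 to 2.53 | 17% narrower |
| 0.3 | 1.300 | 1.196 | 2.60 to 2.42 | 7% narrower |
| 0.5 | 1.116 | 1.086 | 2.23 to 2.19 | 2% narrower |
| 0.6 | 1.012 | 1.003 | 2.02 to 2.02 | none |
| 0.7 | 0.895 | 0.895 | 1.79 to 1.81 | 1% wider |

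A gender term with no effect costs about 0.1 percentage point of width. The two extra terms move the t critical value from 2.007 to 2.009.

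**Step 3: the estimate.** It would move from +0.24 to 0.80 - 0.5b, that is +0.80 at rho = 0 and +0.30 at rho = 0.7. The shift reflects the chance baseline gap and is not a gain in precision.

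**The case against.** The strongest reply is that nothing here is an error. A time by group test in a mixed model is a legitimate estimator for a study that its own introduction calls a pilot. That stands, and it limits the point to a suggestion about precision.

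Second, a reader might take it as established that the model was unadjusted. The documents do not say so. Taken literally, time plus time by group without a group main effect makes the arms share one baseline mean, which does adjust for baseline. The p-values make that unlikely but do not exclude every specification, and a gender term could have been fitted and not reported.

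Third, because the p-values fit rho near 0, a reader might take 17% as the expected gain. It is not established. If the model ignored pairing and the true rho were 0.5, correct handling of pairing alone would cut the half-width from about 3.07 to 2.23. Baseline adjustment would add only the step to 2.19.

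Fourth, a reader might argue that the entry rule of ISI 15 or more floors the baseline scores and so lowers rho. The Procedure section places eligibility at a screening survey and the baseline surveys later, after consent and receipt of the device. The Figure 2 caption measures response from screening. The documents do not show that baseline-week scores were bounded at 15.

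Fifth, no precision gain from gender can be shown. Table 1 reports sex (68% and 65% female), not the gender variable used for stratification. The case for including gender is consistency with the randomisation.

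**Conclusion.** The point holds as a low-cost improvement to consider. The primary contrast appears to be an unadjusted difference in change. This is an inference from the terms named and from the reported p-values, and it is well supported though not certain.

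A reader might infer that the primary result is biased or that adjustment would reveal a benefit. Neither follows. Randomisation makes the unadjusted contrast unbiased, 19.1 against 18.6 is an ordinary chance gap, and the adjusted 1-month p stays at 0.53 or above over correlations of 0 to 0.7, with the estimate still favouring control.

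The possible gain in CI width runs from about 17% at rho = 0 to none at 0.6, with a loss of about 1% near 0.7. These figures assume the rounded Table 2 SDs, an equal SD in both arms, 25 and 29 observed, and a gender term with no effect. If the fitted model ignored pairing, the 17% is not the true gain from adjustment.

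**What to change.** Keep the existing time by group estimate as the primary result and give its 95% CI. Beside it, labelled post hoc because the results are already tabulated, report the 1-month ISI difference adjusted for baseline ISI, with its 95% CI. Either of two models would serve: a common-baseline mixed model with unstructured covariance, or analysis of covariance.

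State whether the covariate is the baseline-week or the screening ISI. Include gender as recorded for stratification, to match the analysis to the randomisation, and claim no precision gain from it. Alongside, give the full model formula with its covariance structure and the observed baseline to 1-month ISI correlation, so that a reader can see whether adjustment helped.

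The cost is one refit of data already held, two degrees of freedom and a few lines of text. No new data are needed.
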